6.1.3 Primary Efficacy Analysis

Two sample comparison of proportions or patients reaching the primary outcome at one year, unadjusted.

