1.0 BACKGROUND AND RATIONALE

Stroke is a leading cause of death and disability worldwide. In Canada, there are approximately 38,000 ischemic stroke admissions to hospital per year with an average annual cost estimated at 2.8 billion dollars.(1) Cardiac embolism is the cause of approximately 25% of ischemic strokes(2) with majority of these due to atrial fibrillation (AF).(3) Cardio-embolic stroke event rates are projected to rise in the next three decades, as the prevalence of AF increases with an aging population. The diagnosis of AF in stroke patients is particularly important since it typically results in prescription of antiplatelet to oral anticoagulant (OAC) therapies(4) that have been shown to reduce the risk of recurrent stroke by up to 63%.(5)

AF can be difficult to detect as it is often intermittent (paroxysmal) and most patients are asymptomatic.(6) In 25-30% of ischemic strokes no cause is established despite thorough diagnostic workup (cryptogenic stroke). Undiagnosed paroxysmal AF has been hypothesized to be the cause of a substantial proportion of cryptogenic strokes. Furthermore, determining TIA/stroke etiology is imperfect and often is complicated by the presence of coexisting causes.(7) It is likely that a sizable number of patients in whom a TIA/stroke has been attributed to an abnormality other than AF (non-cryptogenic stroke) will have AF detected if adequately investigated with prolonged ECG monitoring.(8)

Given superiority of OAC therapy in secondary stroke prevention in AF, detection of paroxysmal AF in all regardless of putative mechanism is of particular clinical relevance. Intermittent ambulatory electrocardiographic (ECG) assessment (Holter) is typically used for detection of paroxysmal AF after a stroke. However, this approach has a very low diagnostic yield in detecting a clinically actionable ECG diagnosis (4%-6%).(9) Cardiac ultrasound (echocardiography) is also routinely ordered after a stroke, but has a diagnostic yield of only 1% and rarely alters clinical management.

It is typical for a patient to undergo multiple ECGs, Holters and an echocardiogram after a stroke at significant cost (> \$1,000), but low diagnostic yield (< 5%).

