4.0 STUDY OUTCOMES

Primary Outcome

The primary outcome will be the rate of detection of an atrial arrhythmia (AF / atrial flutter) that results in initiation of additional anti-platelet or OAC therapy as per usual clinical practice.

Secondary Outcomes:

1. Recruitment rates.
2. Compliance with assigned therapy (accept ILR, conduct at least 80% of ELR assessments)
3. Time to detection of first episode of atrial fibrillation / atrial flutter \geq 30 seconds.
4. Costs for all cardiac and non-cardiac investigations related to etiologic workup of index stroke / TIA.
5. Total duration of any detected atrial fibrillation / atrial flutter.
6. Study related adverse events / serious adverse events.
7. Clinical recurrence of ischemic stroke / TIA, death, hemorrhagic stroke, major adverse bleeding, or death.
8. Association between baseline clinical characteristics (e.g. comorbidities, burden of supraventricular ectopy on Holter, left atrial dimension) and subsequent detection of AF

OUTCOME REPORT

If a subject experience any of the following a outcome report is to be completed following:

- New TIA – complete GUSTO
- New Ischemic Stroke – complete TOAST
- Intracranial Hemorrhage- Complete Intracranial Hemorrhage classification

- Other Bleeding event- complete GUSTO
- Newly Diagnosed Atrial Fibrillation/Atrial Flutter

Assessment of Adverse Events

All serious adverse events (per GCP guidelines) will be reported and described using the MEDRA classification and categorized as related or unrelated to the treatment strategy.

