Appendix I: Schedule of Assessments

	Pre-study (routine clinical studies)	Baseline (Day 0)	Day 30 (± 1 week)	6 months (± 2 weeks)	12 months +/- 4 weeks (telephone)	24 month +/- 4 weeks (telephone)
Holter (optional)	X	Reports collected				
Echo (optional)	X	Reports collected				
Neuroimaging (CT or MRI)	X	Reports collected				
Vascular Imaging (CTA/MRA/doppler)	X	Reports collected				
ECG	X	Reports collected	X	X		
Informed consent, randomization		X				
Demographics		X				
Medical History		X			X	X
Vital signs		X*	X	X		
Antithrombotic and thrombolytic therapy		X	X	X	X	X
NIHSS		X				
CHA2DS2-VASc		X				
TIA/Stroke Subtype / Etiology (OCSS/TOAST)		X				
Modified Rankin		X		X		
EQ-5D		X		X		
Adverse event assessment		X	X	X	X	X
New stroke/TIA, cardiac events		X	X	X	X	X
Return monitor / compliance diary			X			

*Height and weight will be obtained at this visit only.

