STATISTICAL ANALYSIS PLAN

Post-Embolic Rhythm Detection with Implantable versus External Monitoring (PER DIEM) Study

Feb 2019

Version 1.0

Trial Registration ClinicalTrials.gov Identifier: NCT02428140

Statistical Analysis Plan v1.0

Clarification Note:

The statistical analysis plan v1.0 (SAP) defines the primary outcome using the endpoint from the protocol version 4.0 (dated February 22, 2016). There was an additional amendment to the protocol on April 26, 2016, where the AF adjudication process was specified, and the primary endpoint was defined as **definite AF lasting 2 minutes or more, including atrial flutter**. Version 1.0 of the SAP incorrectly carried forward the primary endpoint based on the Feb 22, 2016 version 4.0 protocol rather than the updated definition of the primary endpoint as approved by the steering committee and amended to the protocol on April 26, 2016.

SIGNATURES OF APPROVAL

[name]., Principal Investigator
University of Alberta Hospital

March 1st, 2019

Date

[name]., Investigator
Director Stroke Unit, Foothills Medical Centre

1 Mar 2019

Date

TABLE OF CONTENTS

	Page
SIGNATURES OF APPROVAL.....	2
TABLE OF CONTENTS	3
LIST OF TABLES.....	4
LIST OF ABBREVIATIONS	5
1.0 INTRODUCTION.....	6
1.1 Background	6
1.2 Primary Objectives.....	6
1.3 Study Design	6
1.4 Sample Size Determination	7
Table 1. Schedule of Assessments.....	8
1.5 Blinding	9
1.6 Definitions.....	9
2.0 ANALYSIS POPULATIONS.....	10
2.1 Intent-to-Treat Population	10
2.2 Per Protocol (PP) Population.....	10
3.0 INTERIM ANALYSES.....	10
4.0 MISSING DATA AND DATA TRANSFORMATION	10
5.0 STATISTICAL METHODS	10
5.1 Protocol Deviations and Protocol Violations.....	11
5.2 Demographic and Baseline Characteristics.....	11
6.0 EFFICACY ANALYSIS.....	11
6.1.1 Primary Outcome	11
6.1.2 Statistical Hypothesis.....	12
6.1.3 Primary Efficacy Analysis.....	12
6.2 Secondary Efficacy Analyses.....	12

LIST OF TABLES

	Page
Table 1. Schedule of Assessments.....	8

LIST OF ABBREVIATIONS

AE	Adverse Event
AIS	Acute Ischemic Stroke
ANCOVA	Analysis of Covariance
CI	Confidence Interval
ECG	Electrocardiogram
EMS	Emergency Medical Services
e-CRF	Electronic Case Report Form
ICH	Intracerebral Hemorrhage
IQR	interquartile range
mRS	Modified Rankin Scale
NCCT	Non-contrast Computed Tomography Scan
NIHSS	National Institutes of Health Stroke Scale
PERDIEM	Post-Embolic Rhythm Detection with Implantable versus External Monitoring (PER DIEM) Study
PP	Per Protocol
SAE	Serious Adverse Event

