1.4 Sample Size Determination

A total of 300 patients will be randomized. This sample size reflects 8% inflation for cross over (2% with either strategy) and loss to follow-up (5% in each group). This sample size provides 85% power to assess a clear difference in rates of atrial arrhythmia (AF / atrial flutter) that results in initiation of additional anti-platelet or OAC therapy between the two strategies (two- sided alpha of 5%). This estimate is based on the following assumptions:

1. Equal allocation (1:1) to ELR for 30 days vs. ILR plus remote monitoring for 12 months.
2. 10% rate of AF / atrial flutter that results in initiation of additional anti-platelet or OAC therapy in the ELR and 20% rate of this endpoint in the ILR plus remote monitoring group.

This estimate was derived using the Two Independent Proportions (Null Case) Power Analysis estimation method (PASS 2012).

Table 1. Schedule of Assessments

	Pre-study (routine clinical studies)	Baseline (Day 0)	Day 30 (± 1 week)	6 months (\pm 2 weeks)	12 months +/- 4 weeks (telephone)	24 month +/-4 weeks (telephone)
Holter (optional)	X	Reports collected				
Echo (optional)	X	Reports collected				
Neuroimaging (CT or MRI)	X	Reports collected				
Vascular Imaging (CTA/MRA/doppler)	X	Reports collected				
ECG	X	Reports collected	X	X		
Informed consent, randomization		X				
Demographics		X				
Medical History		X			X	X
Vital signs	X*		X	X		
Antithrombotic and thrombolytic therapy		X	X	X	X	X
NIHSS		X				
CHA2DS2-VASc		X				
Stroke Subtype / Etiology (OCSS/TOAST)		X	X	X	X	X
Modified Rankin		X		X		
EQ-5D		X		X		
Adverse event assessment		X	X	X	X	X
New stroke/TIA, cardiac events		X	X	X	X	X
Return monitor / compliance diary			X			

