4.0 MISSING DATA AND DATA TRANSFORMATION

All efforts will be undertaken to avoid missing data. No planned imputation will be undertaken.

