5.1 Protocol Deviations and Protocol Violations

5.2 Demographic and Baseline Characteristics

Subject demographic and baseline characteristics will be summarized with descriptive statistics for each treatment group. Demographic variables include, but are not limited to: age, sex, race-ethnicity, weight as determined in hospital (in kg). Baseline characteristics include but are not limited to: prior use of alteplase (tPA), intended first thrombectomy approach (stent retriever or thrombus aspiration

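### Optional gain: the primary one-year comparison is unadjusted; a prespecified age term would change power by about −0.4 to +5 points, depending on an assumed age effect

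*SAP*

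**What the plan says.** SAP 6.1.3 defines the primary efficacy analysis as a two-sample comparison of the proportions "reaching the primary outcome at one year, unadjusted". SAP 6.2 repeats the unadjusted form for the secondary outcome. No covariate-adjusted analysis of the primary outcome appears in either document. Protocol 3.3 describes variable blocks and no stratification by age.

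Both documents expect baseline factors to predict the outcome. Secondary outcome 8 in Protocol 4.0, repeated in SAP 6.1.1, is "Association between baseline clinical characteristics (e.g. comorbidities, burden of supraventricular ectopy on Holter, left atrial dimension) and subsequent detection of AF". Two of its three examples come from Holter and echocardiography, which the schedules of assessments (Protocol Appendix I, SAP Table 1) mark as optional. On missing data, SAP 4.0 says: "No planned imputation will be undertaken".

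Age is in a different position. It is an inclusion criterion (Protocol 3.2), and SAP 5.2 lists it for baseline description: "Demographic variables include, but are not limited to: age, sex, race-ethnicity". The only link the documents draw between age and AF is in Protocol 1.0, where cardioembolic stroke is projected to rise "as the prevalence of AF increases with an aging population". That is a statement about populations, not about new detections in enrolled patients.

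The planning rates in SAP 1.4 are "10% rate of AF / atrial flutter that results in initiation of additional anti-platelet or OAC therapy in the ELR and 20% rate" for the ILR arm. They were set for the therapy-change endpoint. The SAP's Clarification Note says the governing endpoint is "definite AF lasting 2 minutes or more, including atrial flutter", and no rates are given for it.

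**The concern.** If a baseline variable predicts the outcome, leaving it out of the primary analysis gives up some precision, and any chance imbalance stays in the estimate. Here the design does not balance age and the analysis does not adjust for it.

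The predictors named in the plan are poor candidates for the adjustment. Ectopy and left atrial dimension will be missing for some patients, and with no imputation those patients would drop out of the model. Age should be essentially complete.

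What is at stake is efficiency only. The unadjusted test keeps its error rate and is unbiased for the difference in one-year proportions. The question is whether a nearly free change would recover useful power in a trial whose power is lower than stated.

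**Working it through.** **Inputs from SAP 1.4.** 300 patients, 1:1, so n = 150 per arm; p₁ = 0.10 (ELR), p₂ = 0.20 (ILR); two-sided α = 0.05; stated power 85%; 8% inflation, so 300 × 0.92 = 276, or 138 per arm. **Assumed:** the strength of the age effect, shown as a range.

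**Step 1: the plan's own figure.** Pooled two-proportion test:

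- SE₀ = √(2 × 0.15 × 0.85 / 150) = 0.0412
- SE₁ = √((0.09 + 0.16) / 150) = 0.0408
- z = (0.10 − 1.96 × 0.0412) / 0.0408 = 0.47, so power = 68.1%

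The unpooled version gives 68.8%. At 138 per arm the pooled figure is 64.4%. The stated 85% does not reproduce; it needs 228 per arm. Any gain from adjustment therefore starts from about 68–70%.

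**Step 2: analytic gain.** Take age as a standard normal covariate in a logistic model with the same slope in both arms, and intercepts that keep the marginal rates at 10% and 20%. Let m₁ and m₂ be the age-specific risks, v₁ and v₂ their variances and c their covariance. For a total of 2n patients the variance of the risk difference is V/(2n), where

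- unadjusted: V = 2(0.09 + 0.16) = 0.500
- standardised: V = 2[(0.09 − v₁) + (0.16 − v₂)] + (v₁ + v₂ − 2c)

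AUC 0.61 (log-OR 0.399 per SD): v₁ = 0.00131, v₂ = 0.00398, c = 0.00228. V = 2 × 0.24471 + 0.00073 = 0.4902. Relative efficiency is 0.500/0.4902 = 1.020, equivalent to 153 per arm. Pooled power goes from 68.1% to 69.0%, **+0.9 points**.

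AUC 0.75 (log-OR 1.015 per SD): v₁ = 0.00853, v₂ = 0.02195, c = 0.01348. V = 2 × 0.21952 + 0.00352 = 0.4426. Relative efficiency is 1.130, equivalent to about 169 per arm. Pooled power goes from 68.1% to 73.4%, **+5.3 points**.

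**Step 3: simulation.** 20,000 trials per setting, 150 per arm, Monte Carlo error about 0.3 points per power figure. Adjusted: logistic model with arm and linear age, standardised risk difference, influence-function SE with an n/(n−p) correction. Comparator: unpooled Wald test.

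| Log-OR per SD | Age AUC | Unadjusted | Adjusted | Variance cut |
|---|---|---|---|---|
| 0 | 0.50 | 69.7% | 69.5% | −0.3% |
| 0.25 | 0.57 | 70.0% | 70.0% | 0.5% |
| 0.4 | 0.61 | 70.0% | 70.6% | 1.8% |
| 0.6 | 0.66 | 69.7% | 71.6% | 4.0% |
| 0.8 | 0.71 | 69.4% | 72.1% | 7.0% |
| 1.0 | 0.75 | 69.2% | 74.1% | 10.4% |

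Repeat runs of the same setting gave −0.3 and −0.4 at AUC 0.50, and +4.7 to +5.3 at 0.75. Type I error with 5, 10, 15 or 20% in both arms was 5.0–5.4% adjusted and 4.9–5.3% unadjusted.

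For scale, if the SD of age is 15 to 10 years (assumed), log-OR 0.4 per SD is an odds ratio per 10 years of exp(0.4 × 10/15) = 1.3 to exp(0.4) = 1.5. Log-OR 1.0 is 1.9 to 2.7. In patients, a 7.0% variance cut is worth 300/0.930 − 300 ≈ 23 and a 10.4% cut 300/0.896 − 300 ≈ 35.

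**Step 4: other rates.** The governing endpoint has no stated rates, so the gain was also computed elsewhere:

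| Rates (per arm) | AUC 0.50 | 0.61 | 0.75 |
|---|---|---|---|
| 5% vs 10% (150) | −0.3 | +0.1 | +2.2 |
| 7.5% vs 15% (150) | −0.3 | +0.2 | +4.2 |
| 15% vs 30% (150) | −0.3 | +0.5 | +3.9 |
| 5% vs 15% (150) | −0.3 | +0.3 | +2.8 |
| 15% vs 25% (150) | −0.3 | +0.9 | +6.2 |
| 10% vs 20% (138) | +0.2 | +1.0 | +5.4 |

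**Step 5: age effect differing by arm** (10% vs 20%, ELR/ILR log-OR per SD): 0/1.0 gives +0.9; 1.0/0 gives +0.6; 0.4/1.0 gives +2.3; 0/0.6 gives +0.3.

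**Step 6: if time-to-event were primary.** 4,000 trials per setting, 10% vs 20%, with all ELR detections inside 30 days as a limiting case, and log-HR per SD of age 0 / 0.72 / 0.9. Adding age to a Cox model moves power from 59.1 to 59.0%, 57.2 to 56.0% and 60.8 to 57.6%. In the same trials the comparison of proportions moves from 70.1 to 69.8%, 68.5 to 71.6% and 70.9 to 76.0%. The advice does not carry over to Cox regression.

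**The case against.** The case against raising this is reasonable. The unadjusted test is valid and was chosen explicitly. The size of the gain rests on an input the documents do not contain: age is not among the predictors named in secondary outcome 8, and the 5-point end needs an odds ratio near 2 or more per 10 years. It also needs a strong effect of similar size in both arms, although one arm is monitored for 30 days and the other for 12 months; with unequal slopes the gain was +0.3 to +2.3. Even the best case leaves power near 74%. SAP 5.0 names time-to-event for the primary outcome and SAP 6.1.2 states the hypothesis as a hazard ratio, and under that reading the advice falls away. Finally, the SAP was signed in March 2019 for an open-label study, so the time for a clean amendment may have passed.

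All of this stands as a limit on importance. None of it makes the point wrong. The loss if age is not prognostic is a few tenths of a point, against a possible gain of several points, and unequal slopes still leave a small gain. The dependence on the primary method and on timing is handled by making the fix conditional.

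**Conclusion.** The point holds as a low-priority, optional improvement. At 10% versus 20% with 150 per arm, adjusting the comparison of proportions for age changes power by about −0.4 to +5 points for an age AUC of 0.50 to 0.75. The change is about 1 point or less at 0.61 or below, and about 3 to 5 points at 0.71 to 0.75. Type I error stays near 5%.

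This rests on an assumed age effect, linear on the logit scale and similar in the two arms, on planning rates set for the superseded endpoint, and on proportions being the primary method. Two neighbouring problems matter more and are not solved by it: the 85% power that does not follow from its inputs, and the conflict over the primary method.

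**What to change.** 1. Reconcile SAP 5.0, 6.1.2 and 6.1.3 so that one primary method is named.
2. If it is the comparison of proportions, replace the unadjusted specification in 6.1.3 with text such as: *Risk difference at one year, standardised from a logistic model with arm and baseline age (continuous, linear), with a robust (influence-function) standard error and small-sample correction. The unadjusted two-proportion comparison is a sensitivity analysis.*
3. Make the change by dated SAP amendment before any comparison of outcomes by arm. If such a comparison has been seen, keep the unadjusted test as primary and report the age-adjusted result as a labelled supportive analysis.
4. If time-to-event becomes the primary method, do not make this change.

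The cost is one SAP sentence and a few lines of code in the named software, with no new data. If age turns out not to be prognostic, the loss is about 0.2 to 0.4 power points.

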6.2 Secondary Efficacy Analyses

Two sample comparison of proportions or patients reaching the secondary outcome at one year, unadjusted.

Time to event analysis on the primary and secondary outcome.

Safety analyses by proportion of adverse events.
